### 4. STATISTICAL ANALYSES

## 4.1. General Considerations

## 4.1.1. General Methodology

Confidence intervals will use 95% confidence levels.

The group GMC ratio will be based on a back transformation of group contrast in an ANCOVA model applied to the logarithm- transformed titers.

Primary analysis: The ANCOVA model will include the treatment group and the age category (age at vaccination: 60-69, 70-79 or ≥80 years) as fixed effects and the pre-dose log-10 titer as covariate.

Sensitivity analysis: The ANCOVA model will include the treatment group and the age category (age at vaccination: 60-69, 70-79 or ≥80 years) and the center as fixed effects and the pre-dose log-10 titer as covariate.

95% CI for GMC will be based on a back transformation of CI for the mean of log-transformation.

The equivalence will be shown if the 95% CIs of the geometric mean concentration (GMC) ratio of each lot over the each other lot is inside the acceptance limit 0.67-1.5 for the antibody concentration 30 days post vaccination (day 31).

95% CI for proportion will be based on exact [Clopper,1934] Pearson CI.

Summary results will be presented by group for immunogenicity and safety and by group and in total for demographic characteristics (pooling of the 3 groups).

#### 4.1.2. Baseline Definition

For all endpoints, the baseline value will be the pre-dose assessment with a non-missing value, including those from unscheduled visits. If time is not collected, Day 1 assessments are assumed to be taken prior to first dose and used as baseline.

Unless otherwise stated, if baseline data is missing no derivation will be performed and baseline will be set to missing.

## 4.2. Primary Endpoint(s) Analyses

## 4.2.1. Definition of endpoints

## 4.2.1.1. Immunogenicity endpoint

The GMC ratios will be computed for each pair of RSVPreF3 OA investigational vaccine lots (RSVPreF3\_Grp1 versus RSVPreF3\_Grp2, RSVPreF3\_Grp1 versus RSVPreF3\_Grp3, RSVPreF3\_Grp2 versus RSVPreF3\_Grp3).

## 4.2.2. Main analytical approach

The primary analysis of lot-to-lot consistency will be performed on the PPS for immunogenicity.

If in any study group the percentage of vaccinated participants with serological results excluded from the PPS is more than 5%, a second analysis based on the Exposed Set (ES) will be performed to complement the PPS analysis.

The 3 RSVPreF3 OA investigational vaccine lots will be compared in terms of RSVPreF3 IgG-specific antibody concentrations at 1-month post-vaccination, with a 1-sided alpha of 2.5%.

The 2-sided 95% CI for group GMC ratio will be derived from an ANCOVA model\* on log10 transformed titer.

\* Primary analysis: The model will include the treatment group and the age category (age at vaccination: 60-69, 70-79 or ≥80 years) as fixed effects, and the pre-dose log10-transformed titer as covariate. Sensitivity analysis: The model will include the treatment group and the age category (age at vaccination: 60-69, 70-79 or ≥80 years) and center as fixed effects, and the pre-dose log10-transformed titer as covariate. Missing data will not be replaced. Titers below the assay cut-off will be replaced by half the assay cut-off, titers above the upper limit of quantification (ULOQ) will be replaced by the ULOQ.

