4.1.1. Overview of recruitment plan

No screening visit is planned for this study. The study is planned to be conducted at sites in multiple countries. The recruitment plan will be defined by each participating site.

The recruitment plan may be adapted based on the actual number of participants enrolled in each country. In case a site would fall behind in participant recruitment, a redistribution of the enrolment target per site in the participating countries may be made. This would allow the other participating sites to enroll additional participants to ensure full and timely enrolment of the overall targeted number of participants specified in this protocol.

The procedures for participants identification/recruitment must be approved by the Independent Ethics Committee (IEC)/Institutional Review Board (IRB) together with the material intended for participants identification/recruitment and participants use. Refer to the Study Procedures Manual (SPM) for additional details.

^{*}GSK central study team will be unblinded to the data at the time of final analysis in order to prepare the Clinical Study Report of the final analysis. The study participants will remain blinded until the study end.

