6.3.3. Intervention allocation to the participant

An automated Internet-based system, Source data Base for Internet Randomization (SBIR) will be used for randomization and for identification of intervention material.

The randomization algorithm will use a minimization procedure accounting for age (60 to 69, 70 to 79 or \geq 80 years) and center. Minimization factors will have equal weight in the minimization algorithm. Refer to Section 4.1.2 for the enrolment rules.

The 3 study groups for the lot-to-lot evaluation will receive adjuvanted vaccine consisting of unique combinations of RSVPreF3 antigen lots, i.e., Lot 1, Lot 2, or Lot 3, and extemporaneously reconstituted with AS01_E adjuvant lots, i.e., Lot A, Lot B, and Lot C.

217131 (RSV OA=ADJ-009) Protocol Final

One of the combinations of the $AS01_E$ adjuvant lot and RSVPreF3 antigen lot will be in alignment with the RSV OA=ADJ-006 study (efficacy study). The 2 remaining adjuvant lots will be randomly combined with the 2 RSVPreF3 antigen lots. The random assignment will be done using the RAND function, that uses the Mersenne-Twister algorithm. Details of the study groups and antigen/adjuvant lots are presented in Table 5 and Table 6.

Once a participant identification number is allocated, the randomization system will determine study group and will provide the study intervention number to be used.

When SBIR is not available, please refer to the SBIR user guide or SPM for specific instructions.

Refer to the SPM for additional information relative to the intervention number allocation.

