9.3.1. Primary endpoint analysis

The primary analysis of lot-to-lot consistency will be performed on the PPS for immunogenicity (PPSi).

If in any study group the percentage of vaccinated participants with serological results excluded from the PPSi is more than 5%, a second analysis based on the Exposed Set (ES) will be performed to complement the PPSi analysis.

The 3 RSVPreF3 OA investigational vaccine lots will be compared in terms of RSVPreF3 IgG-specific antibody concentrations at 1-month post-vaccination, with a 1-sided alpha of 2.5%. The 95% CIs of the GMC ratios will be computed for each pair of RSVPreF3 OA investigational vaccine lots (RSVPreF3_Grp1 versus RSVPreF3_Grp2, RSVPreF3_Grp1 versus RSVPreF3_Grp3, RSVPreF3_Grp2 versus RSVPreF3_Grp3) using an analysis of covariance (ANCOVA) model on the log transformation of the RSVPreF3 IgG concentrations. The ANCOVA model will include the vaccine group and the age category (60 to 69 years, 70 to 79 years, \geq 80 years) as fixed effect and the baseline antibody concentration as covariates.

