## 4.2.3. Sensitivity analyses

Not Applicable

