## 4.6. Changes to Protocol Defined Analyses

Not applicable.

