### Primary Objectives:

- **Endpoint:** RSVPreF3 IgG specific antibody concentration at 1-month post-vaccination (Day 31).
- **Group level summary:** Antibody geometric mean concentration (GMC) per group.
- Reference for the sample size calculation: A standard deviation (SD) of the log10-transformed concentrations of 0.45 is used as reference. It is the highest SD observed in the RSV OA=ADJ 002 (208851) study among all treatment groups and humoral assays.
- Success criteria for consistency: the 2 sided 95% confidence interval (CI) of the GMC ratios between each pair of the 3 lots is within the pre-defined clinical limit of [0.67, 1.5].
- **Null hypothesis:** At least 2 of the 3 vaccine lots differ by more than 1.5-fold (1 sided non-inferiority limit) with respect to their GMC.

- **Alternative hypothesis:** Clinical equivalence (consistency) between each pair of the 3 lots with respect to their GMCs.
- **Type I error:** a 1-sided alpha of 2.5% will be used for the 6 non inferiority tests, no adjustment of Type 1 error is needed because all the lot-to-lot consistency criteria have to be met simultaneously
- **Type II error:** Considering a Bonferroni correction for multiplicity, the global Type II error will be equal to 6 time the nominal Type II error calculated for one non inferiority test. The sample size is determined to reach a global power of at least 90%.

Table 2 shows that the probability (global power) to reach the lot-to-lot consistency criterion with 225 evaluable participants in each vaccine lot group is at least 91%, with a 1-sided alpha = 0.025.

Table 2 Power to demonstrate consistency between each pair of the 3 lots in terms of RSVPreF3 IgG GMCs with 225 evaluable participants per group

Vaccine component	Endpoints	Reference SD*	Clinically acceptable bounds for consistency	N per group	1-sided alpha	Power	Type II error
RSVPreF3 IgG-specific	GMC	0.45	[0.67, 1.5]	225	0.025	91%	9%

GMC: geometric mean concentration; Ig: immunoglobin; N = number of participants; SD: Standard Deviation (of the log10 transformed concentration)

Pass 2019 (Non-Inferiority test of 2 independent means). Power = 100-the Type II error (Beta). The Type II error (Beta) has been adjusted using Bonferroni's method (overall Type II error = sum of the individual Type II errors) since 6 non-inferiority tests are needed for lot-to-lot consistency (nominal Beta for each non-inferiority test is 1.5%).

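### Allocation is minimized on age and center, but the primary ANCOVA leaves center out; the lot-ratio intervals are somewhat too wide if centers differ, and SAP 4.2.3 omits the center model

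*SAP*

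**What the plan says.** Protocol 6.3.3 uses minimization with two factors, age category (60-69, 70-79, 80 and over) and center: "Minimization factors will have equal weight in the minimization algorithm".

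Protocol 9.3.1 sets the primary model: "The ANCOVA model will include the vaccine group and the age category", with baseline antibody concentration as covariate. SAP 4.2.2 repeats it: "The model will include the treatment group and the age category (age at vaccination: 60-69, 70-79 or ≥80 years) as fixed effects", again with the pre-dose log10 value as covariate. Neither has a center term, and no reason is given for keeping one minimization factor and dropping the other.

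SAP 4.1.1 and 4.2.2 also specify a sensitivity ANCOVA with treatment group, age category "and the center as fixed effects and the pre-dose log-10 titer as covariate". The SAP version history shows that amendment 1 added a sensitivity analysis at the FDA's request; the center model is the only one so labelled. Yet SAP 4.2.3 (Sensitivity analyses) and SAP 4.6 (Changes to Protocol Defined Analyses) are both marked not applicable.

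**The concern.** Minimization on center balances the lots within centers, so most between-center variation drops out of the lot contrasts. A model without center still counts that variation in its residual variance. The estimated standard error then exceeds the true sampling error of the contrast, and the 95% interval for each GMC ratio is too wide. This happens only if centers differ after adjustment for age and pre-dose titer; otherwise nothing is lost.

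For an equivalence test the direction is safe: a wider interval fits less easily inside [0.67, 1.5]. At stake is efficiency and agreement between analysis and design, not validity. The single confirmatory objective is decided by the model that does not match the allocation. A reader who goes to SAP 4.2.3 would also conclude that no sensitivity analysis exists.

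**Working it through.** **Inputs from the documents.** Limits [0.67, 1.5], or -0.1739 and 0.1761 on the log10 scale; one-sided alpha 2.5%; 225 evaluable per group; six non-inferiority tests; stated power 91%. On the SD, SAP 5 says "A standard deviation (SD) of the log10-transformed concentrations of 0.45 is used as reference". This is the SD of the concentrations, not a residual SD after covariates.

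**Assumptions.** True lot ratio 1 for the power check, and the center share of residual variance, called s below. Neither the between-center variance nor the number of centers is given, so s is shown as a range that includes zero.

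**Stated power.** SE = 0.45 × √(2/225) = 0.0424. With margin log10(1.5) and the noncentral t, beta is 1.46% per test; 6 × 1.46% = 8.7%, so global power is 91.3%. With the slightly tighter 0.67 limit it is 90.1%. Normal approximations give 91.5% and 90.3%. The stated 91% reproduces without any center term.

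**Interval width and error rate.** Excess width of the primary interval = 1/√(1−s) − 1. One-sided error at the margin = 1 − Φ(1.96/√(1−s)).

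**Joint success over the three pairs.** 1,000,000 draws; n = 225 per lot; residual variance 0.45² including the center part; t quantiles with 669 df without center (675 − 6) and 655 df with center (15 centers assumed, 14 more parameters). Lots equal:

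| Center share s | Primary CI too wide by | One-sided error | Success without center | Success with center |
|---|---|---|---|---|
| 0% | 0% | 2.5% | 92.2% | 92.2% |
| 5% | 2.6% | 2.2% | 93.1% | 93.9% |
| 10% | 5.4% | 1.9% | 94.0% | 95.4% |
| 20% | 11.8% | 1.4% | 95.8% | 97.8% |

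**Check by simulating the allocation.** Minimization on age and center, 675 evaluable participants, 15 centers, both ANCOVAs fitted. At s = 0, 10 and 20%:

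- Coverage with equal lots: primary 95.3, 95.9, 97.2%; center model 95.3, 95.4, 95.3%.
- One-pair error at a true ratio of 1.5: primary 2.4, 1.6, 1.3%; center model 2.4, 2.2, 2.1% (Monte Carlo SE about 0.3 points).

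**Sensitivity to the SD and to true lot differences.**

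- Lots equal, baseline and age assumed to remove 20% of variance: the gain is at most 0.5 points (99.1 vs 99.6% at s = 20%).
- Lots evenly spaced over an assumed 1.15-fold spread on the 0.67 side, residual SD 0.45: gains of 1.9, 3.8 and 7.5 points at s = 5, 10 and 20% (73.9 vs 81.4% at 20%).
- Same spread, baseline and age assumed to remove 40% of variance: gains of 0.7, 1.3 and 2.1 points.

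**Price of adding center when it has no effect.** From the design-matrix variance of the lot contrasts (750 minimized, 10% excluded at random), the interval is about 0.1% wider with 10 centers, 0.2-0.3% with 20 and 0.5-0.9% with 40; these counts are assumed. Since 1/√(1−s) − 1 is about s/2 for small s, center pays for itself once s exceeds roughly 0.2 to 2%.

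**The case against.** The strongest reply is that the center model is already prespecified and will be reported. SAP 4.1.1 and 4.2.2 label the two models plainly as primary and sensitivity, so the entry in 4.2.3 looks like a section that was not updated. The planned power never relied on center adjustment, and success without center stays above 91% in every equal-lots row of the table, so the sponsor only forgoes an optional gain. Baseline titer may absorb part of any center difference. The 7.5-point figure needs a true lot difference, a 20% share and no variance removed by covariates, all at once. Replacing the primary model also departs from the protocol and brings in a pooling decision.

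Most of this stands, and it is why the point is minor. The 7.5-point figure is an upper case, not an expectation, and nobody reading 4.2.2 would mistake which model decides. But the reply does not explain why one allocation factor is kept and the other dropped, and it leaves 4.2.3 in conflict with 4.1.1 and 4.2.2. A pooling rule is useful whichever model is primary, because the planned sensitivity model also has a center term and protocol 4.1.1 says that "a redistribution of the enrolment target per site in the participating countries may be made", so some centers may be small.

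**Conclusion.** The point holds and is minor. If centers differ after adjustment, the primary intervals are too wide: by 2.6 to 11.8% for assumed center shares of 5 to 20%, and not at all if the share is zero. The test is then stricter than its nominal 2.5%. The risk of a false claim of consistency does not rise, and the 91% power is not undermined. With equal lots the forgone gain is 0 to 2 points, and less if baseline and age explain appreciable variance; it is larger only if the lots truly differ. These sizes rest on assumed center shares. The mismatch with the allocation and the conflict over SAP 4.2.3 do not.

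**What to change.** Make the ANCOVA with treatment group, age category, center and pre-dose log10 concentration the primary analysis, and fix a rule for pooling small centers before unblinding. Keep the model without center as the sensitivity analysis and list it in SAP 4.2.3. Record the departure from protocol 9.3.1 in SAP 4.6.

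If the sponsor keeps the present primary model, the SAP should at least say why center is left out and list the center model in 4.2.3. That would settle the documents but leave the mismatch with the allocation.

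The cost is SAP wording, since both models are already specified, plus a recorded departure from the protocol's primary model, about one degree of freedom per center out of about 669, and the pooling rule.

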### **Success criteria for equivalence:**

• The 2-sided 95% CI on the group GMC ratio (RSV PreF3 OA lot divided by another RSVPreF3 OA lot) for RSV investigational vaccine inside [0.67; 1.5]

## 4.2.3. Sensitivity analyses

Not Applicable

## 4.3. Secondary Endpoint(s) Analyses

## 4.3.1. Definition of endpoints

### 4.3.1.1. Immunogenicity endpoints

A seronegative participant will be defined as a participant whose antibody concentration is below the cut-off value of the assay. A seropositive participant is a participant whose antibody concentration is greater than or equal to the cut-off value of the assay.

MGI (mean geometric increase): The geometric mean of the within participant ratios of the post-dose concentration over the pre-dose concentration.

## 4.3.2. Main analytical approach

## 4.3.2.1. Immunogenicity analysis

The primary analysis of secondary immunogenicity endpoints will be based on the PPS for analysis of humoral response. If, in any vaccine group, the percentage of vaccinated participants with serological results excluded from the PPS for analysis of immunogenicity is 5% or more, a second analysis based on the ES will be performed to complement the PPS analysis.

For each group, at each time point that blood samples are collected (unless otherwise specified):

- Percentage of participants above pre-defined assay cut-off and their exact 95% CI will be tabulated.
- GMCs and their 95% CI will be tabulated and represented graphically.
- MGI will be tabulated with 95% CI.
- Antibody titer/concentration will be displayed using reverse cumulative curves.

The above mentioned descriptive within group immunogenicity analysis will also be generated by age at first vaccination (60-69, 70-79,  $\geq$  65,  $\geq$  70 and  $\geq$ 80 years).

### 4.3.2.2. Safety analysis

The safety analysis will be performed on the ES as follows:

• The number and percentage of participants and doses with at least one administration site event AE (solicited and unsolicited), with at least one systemic AE (solicited and unsolicited) and with any AE during the 4-day and 30-day follow-up period will be tabulated with exact 95% CI after vaccination. The same computations will be done

for Grade 3 AEs, for Grade 3 non-serious AEs and for AEs resulting in a medically attended visit.

These analyses will present all solicited and unsolicited AEs, including SAEs and pIMDs (unless otherwise specified).

The above analysis will also be performed for the solicited symptoms only during the 4-day follow-up period.

- The number and percentage of participants reporting each individual solicited administration site AE (any grade, Grade 3 and resulting in medically attended visit) and solicited systemic AE (any grade, Grade 3 and resulting in medically attended visit) during the 4-day follow-up period (i.e. the day of vaccination and 3 subsequent days) will be tabulated for each group after each dose and overall. The percentage of doses followed by each individual solicited administration site AE (any grade, Grade 3 and resulting in medically attended visit) and solicited systemic AE (any grade, Grade 3 and resulting in medically attended visit) during the 4-day follow-up period (i.e. the day of vaccination and 3 subsequent days) will be tabulated, with exact 95% CI.
- For fever, the number and percentage of participants reporting fever by half degree (°C) cumulative increments during the 4-day follow-up period (i.e. the day of vaccination and 3 subsequent days) will be tabulated for each group after the study dose.
- The percentage of participants with each solicited administration site event and solicited systemic event (any grade and Grade 3) will be represented graphically for each group after the study dose.
- The number of days with solicited events reported during the 4-day follow-up period will be tabulated for each individual solicited event using descriptive statistics (mean, minimum, Q1, median, Q3, maximum). The same computations will be done for Grade 3 solicited events.
- The number and percentage of participants with any unsolicited AEs during the 30-day follow-up period (i.e. the day of vaccination and 29 subsequent days) with its exact 95% CI will be tabulated by group and by Medical Dictionary for Regulatory Activities (MedDRA) preferred term. Similar tabulation will be done for Grade 3 unsolicited AEs, for any causally related unsolicited AEs, for Grade 3 causally related unsolicited AEs and for unsolicited AEs resulting in a medically attended visit. The verbatim reports of unsolicited AEs will be reviewed by a physician and the signs and symptoms will be coded according to the MedDRA. Every verbatim term will be matched with the appropriate Preferred Term.
- The number and percentage of participants with at least one report of SAE classified by the MedDRA Preferred Terms and reported after vaccine administration (Day 1) up to study end (6 months after vaccination) will be tabulated with exact 95% CI.
- The number and percentage of participants with at least one report of causally related SAE classified by the MedDRA Preferred Terms and reported after vaccine administration (Day 1) up to study end (6 months after vaccination) will be tabulated with exact 95% CI.

- The same tabulation will be presented for fatal SAEs.
- All SAEs will also be described in detail in a tabular listing.
- All pIMD will also be described in detail in a tabular listing.
- All AEs/SAEs leading to study/intervention discontinuation from dose 1 up to study end will be tabulated.
- The percentage of participants with at least one report of pIMD classified by the MedDRA Preferred Terms and reported after vaccine administration (Day 1) up to study end (6 months after vaccination) will be tabulated with exact 95% CI. The percentage of participants with at least one report of related pIMD classified by the MedDRA Preferred Terms and reported after vaccine administration (Day 1) up to study end (6 months after vaccination) will be tabulated with exact 95% CI.
- The number and percentage of participants using concomitant medication (any medication and any antipyretic) during the 4-day and the 30-day follow-up period after the study dose will be tabulated with exact 95% CI.
- Compliance in completing solicited events information will be tabulated after the study dose.
- Some of the key safety analysis will be generated by age group at first vaccination  $(60-69, 70-79, \ge 65, \ge 70 \text{ and } \ge 80 \text{ years})$  as mentioned below.
  - The number and percentage of participants reporting each individual solicited administration site AE (any grade, Grade 3 and resulting in medically attended visit) and solicited systemic AE (any grade, Grade 3 and resulting in medically attended visit) during the 4-day follow-up period (i.e. the day of vaccination and 3 subsequent days) will be tabulated for each group after the study dose.
  - The number and percentage of participants with any unsolicited AEs during the 30-day follow-up period (i.e. the day of vaccination and 29 subsequent days) with its exact 95% CI will be tabulated by group and by MedDRA preferred term.
- For clinicaltrials.gov and EudraCT posting purposes, percentage of participants of combined solicited and unsolicited non-serious adverse events during the 30-day follow-up period (i.e. the day of vaccination and 29 subsequent days) will be produced by System Organ Class and preferred terms and according to occurrence of each event.

